**Table 2. Instruments (Logs)**

Variable	Instrument	Measurement
Maternal Factors	Log maintained by Project Coordinator	Age, parity, diabetes, pregnancy induced hypertension, mode of delivery, type of anesthesia, experience with breastfeeding, smoking, obesity, antenatal steroids
Lactation Factors (1-3 below)		
1. Onset of lactogenesis stage II	Log maintained by Project Coordinator	Date and time of sensation of breast fullness Corresponding breast milk measurement
2. Milk volume	Log maintained by Project Coordinator	Daily total breast milk weight for days 1-7 24 hour sample weekly
3. Milk volume alternative for breastfed infants	Log maintained by Project Coordinator	(Test weighing) - difference in infant's weight before and after feeding as indicator of breast milk intake.
Behavioral Factors	Log maintained only by mother	Date and time of pumping sessions, episodes of lactation support. Kangaroo Care log will be maintained separately (see below).
Kangaroo care	Log maintained by nurse or mother	Incidence and length of kangaroo care in min.
Infant breast milk intake (1-2		

below)		
1. Weekly percentage of breast milk received by infant during first 6 weeks of life	Log maintained by Project Coordinator	Data extracted from medical record
2. Percentage of breast milk feedings at discharge	Log maintained by Project Coordinator	Data extracted from medical record

Mothers in all groups will be instructed to record daily in the Maternal Behavioral Factors log book the following data: number of expression sessions per day, the date and time of each pumping session, and whether they received lactation assistance (Appendix F). The frequency of milk expression will be verified by the research coordinator by documentation of the date and time of each vial of milk brought to the NICU. Kangaroo care is encouraged in this NICU and nursing protocols have been established to provide support to all mothers regarding provision of kangaroo care. Infants are also encouraged to suckle at the breast during kangaroo care. Episodes and duration of kangaroo care between mother and infant will be recorded on the Kangaroo Care log sheet (Appendix G) located at the infant's bedside by either the mother or the nurse. While control of these variables within the study is impossible, we will carefully document these behavioral factors to allow for inclusion in statistical analysis as adjustment variables.

Beginning 24 hours after delivery and continuing daily, mothers will be questioned (either in person or over the phone) regarding a sudden feeling of fullness in their breasts as an indicator of the onset of lactogenesis II (Appendix H). This has been a traditional method of determining the timing of lactogenesis stage II and has been shown to correlate with actual timing of this stage (Chapman, Perez-Escamilla, 2000; Perez-Escamilla & Chapman, 2000). Due to the effects of anesthesia, post op pain, and pain medication, mothers may have difficulty appreciating indicators of the onset of lactogenesis stage II, we will therefore confirm the reliability of self-report by determining whether >100mL of milk is produced per a 24-hour period (Neville, Morton, & Umemura, 2001). Since it is anticipated the onset of lactogenesis stage II will occur during the first 7 days, the number of hours post-delivery until lactogenesis stage II will be captured and recorded by research team members in the Milk Volume log.

Prior to discharge, at day 21 and 42, mothers will be asked to complete the MAACL-R. The MAACL-R is a standardized instrument with well-documented psychometric properties that assesses mood states by using positive and negative mood states scales for Anxiety, Depression, Hostility, Positive Affect and Sensation Seeking. It consists of 132 adjectives that are at or below an 8th grade reading level and takes approximately 3 minutes to complete. This test has been successfully used by the consultant for this project in lactating mothers of premature infants (Hill et al 2006; Lubin and Zuckerman, 1999). Mothers will be phoned by the research coordinator the day before the scheduled testing day to remind them to complete the test. The written test that will be completed following discharge will be provided to the mothers upon study entry. Mothers will return the test when they visit their infant and results will be hand scored and recorded on the MAACL-R Result Log by either the RA or the research coordinator. The test and grading sheet will be purchased with institutional funds upon initiation of this project.

Prior to discharge it will be determined whether mothers are continuing to express breast milk. This will be determined by whether mothers are bringing expressed breast milk to the NICU for infant consumption. If they are no longer expressing breast milk, they will be contacted to determine whether they would be willing to participate in a 10 minute interview concerning reasons for cessation of breast milk expression and their feeling concerning cessation of lactation. If interested, an appointment will be made for the interview during a time when the mother will be present in the hospital visiting her infant and a ~~RA who is a~~ licensed registered nurse will ask the mother (5) questions (see addendum S). Should the mother find this to be a stressful topic, the interview will cease immediately and a social worker employed in the neonatal intensive care unit experienced with caring for mothers of premature infants will be immediately notified and will assess whether further services are required.

The percentage of breast milk the infant receives weekly and the percentage of breast milk the infant is receiving upon discharge (mL/kg/d for the week prior to discharge) will be collected from the medical records (Appendix J). Neonatal nurses and physicians caring for the infants will not be told of the mother's assigned group.

## Exploratory Aim 1

Exploratory Aim 1 is to examine the effect of timing of initiation of breast milk expression on infant breast milk intake (e.g., weekly percentage of breast milk the infant receives during hospitalization and amount of breast milk infant is being fed at discharge). This information will be collected from the infant's medical records.

### **Exploratory Aim 2**

Exploratory Aim 2 is to examine the effect of timing of initiation of breast milk expression on milk volume and lactogenesis stage II in mothers who deliver at an earlier gestation (23-27 weeks) and those who delivery at a later gestation (28-32 weeks). Information will be collected according to the procedure in Aim 1.

### **Equipment**

A simultaneous electric Symphony Breastpump ® (Medela, Inc.) will be used during hospitalization, and infant visitation and the same pump will be provided to all mothers enrolled in the study for home use while their infant is hospitalized. These are hospital-grade pumps that can be used for simultaneous breast milk expression (both breasts at the same time). Milk will be weighed on a Scout Balance electronic scale, a portable digital scale accurate to within 0.1 grams (Scout Balance, Florham Park, NJ). The scale contains an external calibration mechanism, stabilizes within three seconds, and will be calibrated by the research assistant prior to initiation of the study and after every 10 measurements using 0.1mg, 1mg, 10mg and 50 mg weights. All weights will meet or exceed American National Standards Institute (ASTM) specifications and will be calibrated by a National Institute of Standards and Technology (NVLAP) accredited lab. The scale will be placed on the same platform at all times and will be wiped clean with a moist cloth and dried between each weighing.

### **Statistical Analysis**

Descriptive Statistics. Descriptive statistics will be calculated for all variables, as appropriate. Continuous demographic and baseline clinical variables will be compared using t-tests or Wilcoxon rank sum tests. Categorical variables will be compared using chi-square or Fisher's Exact Test. Sample distributions will be evaluated to ensure that distributional assumptions underlying the proposed statistical tests have been met.

#### Design/Analysis Issues.

Analysis sets. For primary analyses the intent-to-treat (ITT) sample will be used comprising all randomized mothers patients. Secondary per-protocol (completer) analysis will include mothers who were compliant with protocol requirements and for whom all required measurements have been made. ITT and per-protocol analyses will be compared to test the sensitivity of our conclusions to non-adherence/attrition.

Missing data. Every attempt will be made by the study coordinator to keep mothers in the study, with the help of the student research team members and to obtain required measurements in order to ensure the completeness of the study data. To minimize potential bias due to missing observations, mothers will be contacted by phone if vials of expressed breast milk are missed, and reasons for missing data will be carefully documented. Subject participation will only be terminated due to safety reasons for mother and infant, withdrawal of consent, or loss to follow-up. Several approaches to handle missing data in the ITT analysis set will be employed. For continuous variables using a single end-of-study value (e.g., amount of milk expressed at day 42), Little and Rubin's multiple imputation methods will be used (Little & Rubin, 1997). For analyses of longitudinal outcome data, we will use longitudinal methods (e.g. mixed models) capable of dealing with missing data (Hedeker & Gibbons, 2006).

Multiple outcome variables. In order to address possible Type I errors due to the number of outcome variables, we specify the primary outcome measures a priori corresponding to the stated a priori hypothesis and maintain the alpha (significance) level at 0.02. For analysis of secondary outcome variables, we will further adjust resulting p-values using Bonferroni-type corrections for multiple outcomes. Both unadjusted and adjusted p-values will be reported.

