Measurement of milk volumes by weight will occur at the initial expression session, for the first 7 days, and for one 24-hour period on weekly until the infant is discharged from the hospital. (see Table 2 for a list of all instruments). If the infant breastfeeds during the 24-hour period, test weighing will be used to calculate breast milk consumed. Test weighing or the weighing of infants prior to and following breastfeeding, has been shown to be an accurate method of determining intake during breastfeeding in preterm infants (Haase, Barreira, Murphy, Mueller, & Rhodes, 2009; Hurst, Meier, & Engstrom, 2004). Prior to each breastfeeding session, infants will be weighed by the nurse assigned for patient care, and weight will include the clothing, diaper and/or blankets infant is wearing. Following completion of the breastfeeding session, the infant will be weighed again, clad in the same clothing as with initial weight. Infants will be weighed on the Baby Weigh scale (Medela, Inc, McHenry, IL) to the nearest 0.2 g. The Baby Weigh scale is a portable electronic digital scale that is accurate to within 0.2 grams. The scale will be calibrated by the study coordinator prior to initiation of the study and after every 10 measurements, using 0.2mg, 1 mg, 10mg and 50 mg weights. All weights will meet or exceed ASTM (American National Standards Institute) specifications and will be calibrated by a NVLAP (National Institute of Standards and Technology) accredited lab. The difference between the pre and post-feeding weights will be recorded on the Breastfeeding Data Collection Form taped at the infant's bedside and will be added to the total amount the mother expressed during that 24-hour period (Appendix E).

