### **Analyses for Aim 1**

The primary efficacy outcomes are amounts of breast milk expressed over the first 7 days post-initiation; days 14, 21, 28, 35, and 42 days post-initiation and weekly, and number of days to achieve lactogenesis stage II. To examine expressed breast milk amount over time (i.e. production of breast milk immediately after initiation and subsequently, volume measured daily over the first 7 days and on days 14, 21, 28, 28, and 42 post-initiation and weekly), we will compare the longitudinal profile of milk volume expressed in the three groups over the

study period using mixed effects models (MEM) analyses. These analyses will estimate the average change in breast milk volume within each group (early vs. immediate vs. late initiation) and individual change in breast milk volume for each mother. MEM analyses allow for missing data, measurement of study subjects at different time points during the study, and time varying covariates. MEM can also take into account the effect of clustering, i.e. correlation of repeated breast milk measurements within one subject (Hedeker & Gibbons, 2006; McCulloch & Searle, 2001). The efficacy variable expressed breast milk volume (mL) will be used as the dependent variable with treatment status (early vs. intermediate vs. late initiation), time and time-by-treatment interaction and gestational group (23-27 weeks vs. 38-32 weeks) as primary independent variables. In a second step, additional covariates will be included in the models to adjust for putative predictive variables such as age, mother's weight at delivery, diagnosis of preeclampsia or diabetes, parity, birth weight, weeks of gestation, behavioral factors including skin-to-skin contact ("kangaroo care"), lactation support and mean number of pumping attempts per day. Effect modifications of covariates will be examined through inclusion of a covariate-by-treatment interaction term in the multivariable models. For example, a significant age-by-treatment interaction would suggest that the relationship between treatment and milk volume is different for older mothers compared to younger mothers. Potential key intervening variables such as behavioral factors will be further examined using mediation analysis. Further, the relationship of maternal mood with amount of breast milk will be examined by inclusion of the MAACL-R scores obtained at discharge, days 21 and 42 in the longitudinal MEM model.

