## **Potential Problems and Alternative Strategies**

The most likely potential problem is difficulty retaining subjects in the study between consenting prior to delivery and initial breast milk expression. Although our pilot study indicated this dropout to be highly unlikely, to minimize this problem a member of the research team will be available to the mother to help her pump the first time (at the time designated). Should she chose to pump at a different time (earlier or later), then she will receive the standard care available to her from the nursing staff and will no longer be eligible for the study.

Another problem related to retention is the continued willingness of mothers to express milk at the frequency required and for the duration of the study (at least 5 times a day until attainment of lactogenesis stage II). While this frequency may appear burdensome, these are the standard directions provided to mothers of VLBW infants receiving standard care i.e. who are not enrolled in the study.

A third potential problem is retention of the mother in the study for 6 full weeks post-delivery, when many women stop pumping due to lack of breast milk. To encourage mothers to continue trying to express their milk, each mother will be assigned to a graduate research assistant with experience involving the care of lactating women. This same student RA will contact the mother three times per week, either in person in the hospital or via telephone. The student will remind the mother to continue to pump at least 5 times per day and to bring in her breast milk with every visit. The role of student RAs in maintaining contact with mothers will decrease the likelihood of contamination of data collection procedures, since the PI or one of the co-investigators could inadvertently provide lactation consultation during the calls.

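### The per-protocol set requires complete data, so comparing it with ITT mixes adherence with attrition and does not test drop-out that is missing not at random

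*Combined protocol and SAP*

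**What the plan says.** Under Design/Analysis Issues, the primary analysis is ITT on all randomized mothers. The second set is described as follows: "Secondary per-protocol (completer) analysis will include mothers who were compliant with protocol requirements" and "for whom all required measurements have been made". Its purpose is then stated: "ITT and per-protocol analyses will be compared to test the sensitivity of our conclusions to non-adherence/attrition".

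For missing data in the ITT set, the plan says that for single end-of-study values "multiple imputation methods will be used", and that for longitudinal outcomes "we will use longitudinal methods (e.g. mixed models) capable of dealing with missing data". Reasons for missing data are to be documented, but no analysis is said to use them.

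Under Analyses for Aim 1, milk volume is a primary outcome: "The primary efficacy outcomes are amounts of breast milk expressed over the first 7 days post-initiation", followed by weekly points to day 42. Under Potential Problems and Alternative Strategies, the protocol explains why six-week retention is hard: "many women stop pumping due to lack of breast milk". The measurement procedure under Primary Aim continues "weekly until the infant is discharged from the hospital".

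The plan does not say whether a mother who has stopped expressing contributes 0 mL or a missing value. It does not list which requirements count as compliance.

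**The concern.** The completer set joins two conditions that answer different questions. Compliance concerns whether the assigned timing was followed. Completeness concerns whether outcome data exist. If the two analyses differ, the reader cannot tell which condition caused it.

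The completeness condition has a second problem. On the protocol's own expectation, low milk volume causes late stopping, so low values of the primary outcome lead to exclusion. If early expression works as the sponsor expects, fewer mothers are lost in the early group, and the completers in the late group are the more heavily selected.

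Mixed models and standard multiple imputation rest on missing at random. Completers require more than that. The threat that the planned ITT analyses leave open is stopping driven by current, unobserved low volume. Moving to a stricter assumption does not examine it. No planned analysis relaxes missing at random, so the statement made about sensitivity to attrition would rest on a comparison unsuited to it.

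**Working it through.** **Inputs from the documents.** Sample Size Determination gives SD 250 mL, difference 125 mL, 60 mothers per group, 13 time points, intra-class correlation 0.5, two-sided alpha 0.02 and 85% power. Sample and Setting gives 5% drop-out.

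**The plan's own figure.** The disputed sentence states no number, so I checked that the planning inputs are usable. For volume, the variance factor for a mean of 13 visits is (1 + 12 × 0.5)/13 = 0.538. With group means at −0.25, 0 and +0.25 SD, the noncentrality is 60 × 2 × 0.25² / 0.538 = 13.9. The three-group F test at 0.02 then has power 0.854. For lactogenesis II, 34.1/55.0 = 0.62 and the exact t test gives 0.849. Both agree with 85%.

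**Check 1: size of the completer shrinkage.** Assume day-42 volume is normal with SD 250 and means m and m + 125. Assume a mother stops with probability p(y) = 1/(1 + exp((y − c)/s)), where c is set so that average stopping over the two arms is 5%, 20% or 40%. The completer mean in each arm is E[y(1 − p(y))] / E[1 − p(y)]. The value of m does not affect the completer difference, because c moves with it. The slope s is an assumption, and a smaller s is steeper. Numerical integration gives these completer differences, with shrinkage from 125 mL:

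| Stopping overall | s = 80 mL | s = 160 mL | s = 300 mL |
|---|---|---|---|
| 5% | 108 (13%) | 116 (8%) | 121 (3%) |
| 20% | 86 (31%) | 101 (19%) | 114 (8%) |
| 40% | 70 (44%) | 91 (27%) | 110 (12%) |

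**Check 2: completers beside a missing-at-random estimate.** Simulation of two arms, 60,000 mothers each, 13 visits, SD 250 at day 42, intra-class correlation 0.5, effect 125 mL. Assumptions: late-arm day-42 mean about 400 mL, volumes truncated at 0 (so the true difference is slightly below 125), stopping only after day 7. The chance of stopping per visit is 30% or 60% when volume is below 100 or 200 mL, and 2% otherwise. A sequential regression stands in for the mixed model or imputation. Day-42 differences in mL:

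| Stopping depends on | Cut-off, chance | Completers, late / early | Truth | Missing at random | Completers | 0 mL after stopping |
|---|---|---|---|---|---|---|
| last observed volume | 100, 30% | 77% / 85% | 123.6 | 124.2 | 109.0 | 127.7 |
| last observed volume | 100, 60% | 68% / 80% | 121.9 | 122.6 | 95.9 | 134.7 |
| last observed volume | 200, 60% | 51% / 69% | 120.3 | 122.6 | 85.6 | 148.0 |
| current unseen volume | 100, 30% | 78% / 85% | 121.7 | 116.9 | 104.9 | 121.4 |
| current unseen volume | 100, 60% | 68% / 81% | 120.7 | 109.3 | 90.1 | 130.0 |
| current unseen volume | 200, 60% | 54% / 71% | 120.5 | 101.6 | 78.4 | 141.9 |
| not on volume | 2% per visit | 90% / 90% | 122.0 | 122.2 | 122.0 | 109.2 |

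The gap between the missing-at-random and completer estimates is what the plan proposes to read. In rows 1–3, where the missing-at-random estimate is sound, it is 15.2, 26.7 and 37.0 mL. In rows 4–6, where that estimate is too low, it is 12.0, 19.2 and 23.2 mL. The two ranges overlap, and in each matched pair the gap is larger when ITT is sound. In rows 4–6 both estimates lie below the truth. With no true effect, every difference was within about 2 mL of zero.

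**The case against.** **Selection on the outcome depends on a coding rule.** The protocol asks for vials from every session whatever the yield, establishes before discharge whether mothers are still expressing, and ends participation only for safety, withdrawal of consent or loss to follow-up. If stopping is recorded as 0 mL, completeness need not exclude low producers. This stands, and the conclusion is conditional on it. The plan gives no such rule, and a stopped mother might still fail an undefined compliance condition.

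**A discrepancy does carry information.** A gap between the analyses signals that drop-out is not completely at random. That stands. It does not show whether the ITT estimate is wrong.

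**False reassurance.** A reader might infer that ITT and completers will agree because both are biased the same way. The calculations do not support this. When stopping followed observed volume, ITT was sound and the two disagreed. When it followed unseen volume, both were low but still 12–23 mL apart.

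**Large attenuation.** A reader might take the upper end, 31–44%, as typical. It needs the steep curve (s = 80). With a mean of 400 mL, the 50% stopping point then lies at about 215 mL for 20% stopping and 388 mL for 40%. The latter is hard to call lack of milk, given that the protocol confirms lactogenesis II at more than 100 mL per 24 hours.

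**Long-stay infants.** A reader might infer that mothers of infants discharged before day 42 are excluded. That is one reading only. Measurement is required until discharge, so such a mother may have every required value, although the analysis section lists days to 42.

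**Conclusion.** The point holds in a limited form. The comparison combines two questions and, unless stopping is coded as 0 mL, uses a set selected on milk volume. It does not test whether conclusions survive missing-not-at-random drop-out, which no other planned analysis addresses either.

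The shrinkage of the completer difference is about 3–13% at the plan's 5% drop-out and about 8–44% at 20–40% stopping. The stopping rates above 5%, the logistic shape and the slopes are assumptions, and the documents give no data to choose among them. The simulated pattern also rests on assumed means and stopping probabilities.

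The documents do not support a conclusion that the primary analysis is invalid. It is ITT on all randomized mothers, the completer set is secondary, and in these set-ups selection weakened a real effect and did not create a false one. This should be corrected, but it does not undermine the trial's main result.

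**What to change.** 1. Remove the completeness condition and define the per-protocol set by the protocol's own adherence requirements, listed explicitly. Potential Problems and Alternative Strategies describes both the assigned first-expression window and a pumping frequency, so the definition should say which of these count. That section also makes mothers who first pump outside the window ineligible, which must be reconciled with ITT on all randomized mothers.

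2. For attrition, on all randomized mothers, state how volume after stopping is handled. Add an analysis in which mothers documented as having stopped expressing contribute 0 mL from then on. Label it as a different estimand, total milk expressed. The last column of the second table shows that this choice alone can move the answer (109–148 mL).

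3. For other missing values, add delta-adjusted multiple imputation over a pre-specified range of deltas, and report where the conclusion changes.

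4. Present the per-protocol result as bearing on adherence, and items 2 and 3 as bearing on attrition.

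The cost is revised SAP wording, one or two extra model runs, and deltas that must be chosen in advance. Little or no new data collection is needed: reasons for missing data, continuing expression and pumping dates are already to be recorded.
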